7.3 Setting

7.3.1 Source Population

The source population for this study will include pregnancies that begin (based on ECD) between 12 August 2024 and 31 March 2032 (or most recent data available at the time of the last data extract).

7.3.2 Inclusion Criteria

Pregnancies among women who meet the following criteria will be eligible for inclusion in the study:

- An ECD between 12 August 2024 and 31 March 2032
- For claims data sources, continuous health plan enrollment with complete medical and pharmacy benefit coverage from 6 months before and including cohort entry (only applicable to the pregnant woman)
- For linked claims-EHR data sources:
 - Pharmacy (but not medical) coverage during the full pregnancy period (as described in [Table 1](#)) will be required to ensure dispensings of cohort defining drugs are captured. (A shorter period of continuous enrollment will be required for linked claims-EHR data sources compared with the claims databases because pharmacy claims will be used primarily for exposure assessment, while covariates will be assessed from the EHR data).
 - Presence of at least one outpatient clinical visit at least 6 months prior cohort entry (to establish a 6-month baseline period for assessment of AD and PN as well as clinical covariates).
- Evidence of moderate to severe AD or PN ascertained using appropriate algorithms

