7.3.6 Study Population

7.3.6.1 Exposure Cohorts and Cohort Entry

[figure not shown]
Based on the sequential cohort design, a series of study cohorts will be established for each gestational week of pregnancy ([Caniglia et al., 2023](#); [Hernández-Diaz S et al., 2023](#)). To ensure capture of exposure to AD/PN treatments prior to the ECD but which remain in the body at ECD, the first gestational week of pregnancy will be extended (prior to ECD) by 5 times the half-life for each AD/PN treatment. For example, since nemolizumab has a half-life of 18.9 days ([Nemluvio PI, 2025](#)), the first gestational week for nemolizumab will begin 95 days (approximately 14 weeks) prior to ECD. The half-life for each AD/PN treatment is provided in [Appendix D](#).

As nemolizumab and the comparator AD/PN treatments are injection drugs that are dispensed at a pharmacy for self-injection, treatment duration will be defined as date of dispensing plus 5 times the half-life of the therapy when a single pre-filled syringe, pen, or autoinjector is dispensed. When multiple units are dispensed, the days' supply will be calculated based on the quantity dispensed and recommended administration schedule; treatment duration will be calculated as the date of dispensing plus the days' supply plus 5 times the half-life of the therapy. A treatment will be considered to be overlapping with the first gestational week of pregnancy if there is at least one dispensing or dose received during the period 5 times the half-life prior to ECD through the end of the first gestational week. At each gestational week, we will first restrict to eligible pregnancies with no administrations or dispensings of nemolizumab or the other AD/PN treatments from 5 times the half-life of the corresponding treatment (e.g., 95 days, or approximately 14 weeks, for nemolizumab) before ECD through the end of the prior gestational week. We will then classify exposure status as exposed to nemolizumab, exposed to other AD/PN treatments, or unexposed based on the pregnancy's receipt of nemolizumab or other AD/PN treatments during that gestational week. Pregnancies among women with claims for both nemolizumab and another AD/PN treatment during the relevant exposure window will be excluded. For exposed pregnancies with more than one dose of the index treatment (e.g., two doses of nemolizumab) during pregnancy, cohort entry will align with the first dose.

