Cohort entry will be set at the date of dispensing in the Nemolizumab Cohort (i.e., the earliest nemolizumab administration date during a pregnancy) and the Other AD/PN Treatment Cohort,

and the corresponding day of gestation among unexposed pregnancies, rounded down to the nearest week. For example, for pregnancies entering the Week 8 Cohort, we will first select all pregnancies with no nemolizumab or other AD/PN treatment from 5 times the half-life before ECD through 7 weeks' + 6 days' gestation. Then, we will assign the pregnancies that receive nemolizumab during Week 8 (8 weeks + 0 days through 8 weeks + 6 days) to the nemolizumab-exposed group, those that received another AD/PN treatment to the other treatment-exposed group, and those that did not receive nemolizumab or another AD/PN treatment during Week 8 to the unexposed group. Cohort entry among the Week 8 nemolizumab and comparator cohorts will be set to 8 weeks' + 0 days. The pregnancies in the Week 8 exposed cohort will no longer be eligible for inclusion in subsequent weekly cohorts. However, the pregnancies in the Week 8 unexposed group will go on to be eligible for inclusion in the Week 9 Cohort, at which point their exposure status would be reassessed during Week 9 (9 weeks + 0 days through 9 weeks + 6 days). A pictorial depiction of this process can be found in Figure 1 and key pregnancy dates can be found in Table 1. If the study size does not permit weekly sequential cohorts, the cohorts may be collapsed into longer (e.g., 2-week, 4-week) intervals as needed.

Figure 1 Sequential cohort design, depicting an example of cohort entry for the Week 7 and Week 8 cohorts

Abbreviations: AD, atopic dermatitis; ECD, estimated conception date; PN, prurigo nodularis

Table 1 Pregnancy dates

Date	Definition
LMP	First day of last menstrual period 0 gestational weeks ^{0/7 days}
Gestational age	Weeks of gestation Anchored by LMP Number of completed weeks elapsed after LMP

Date	Definition
ECD	Estimated as LMP + 14 days 2 gestational weeks ^{0/7 days}
First trimester	Begins at ECD minus 5 times the half-life of the treatment Ends at LMP + 97 days
Second trimester	Begins at LMP + 98 days Ends at LMP + 195 days
Third trimester	Begins at LMP + 196 days Ends at pregnancy outcome
Pregnancy period	Begins at ECD minus 5 times the half-life of the treatment Ends at pregnancy outcome

Abbreviations: ECD, estimated conception date; LMP, first day of last menstrual period

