7.3.6.5 Unexposed Cohort

The Unexposed Cohort will include all pregnancies among women with moderate to severe AD or PN who have no dispensings or administrations of nemolizumab or the other monoclonal antibody treatments used to defined the Other AD/PN Treatment Cohort (i.e., dupilumab, lebrikizumab, tralokinumab) from 5 times the half-life of each medication prior to ECD through the end of pregnancy. The cohort entry date will be matched to the date of nemolizumab dispensing, rounded down to the nearest week of gestation.

This cohort may include pregnancies among women who have dispensings or administrations of other treatments indicated for moderate to severe AD or PN (e.g., immunosuppressants, corticosteroids). Exposure to other treatments for moderate to severe AD or PN will be measured and adjustment for or stratification by use of these treatments may be considered during the analysis.

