7.3.6.6 Baseline Period

The 6 months (183 days; defined as an inclusion criteria) prior to and including the cohort entry date will be set as the baseline period. Recognizing that a narrower (for time-varying covariates, etc.) or a broader (for chronic conditions) window of assessment may better capture patient characteristics of interest, specific covariates may be assessed using alternative time period(s). For example, while patients are required to have 6 months of continuous medical and pharmacy coverage prior to cohort entry to be eligible for inclusion in the study, presence of AD and PN will be assessed up to 12 months prior to pregnancy, as data allow.

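### In claims-only sources, enrolment is anchored on cohort entry but the drug-free window on conception, so the required enrolment does not guarantee that later weekly cohorts have the window fully observed

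*Protocol*

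**What the plan says.** Section 7.3.2 asks claims sources for "continuous health plan enrollment with complete medical and pharmacy benefit coverage from 6 months before and including cohort entry". Section 7.3.6.6 gives the length: "The 6 months (183 days; defined as an inclusion criteria) prior to and including the cohort entry date". Both count back from cohort entry.

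The drug-free requirement counts back from ECD. At each gestational week, 7.3.6.1 will "restrict to eligible pregnancies with no administrations or dispensings of nemolizumab or the other AD/PN treatments from 5 times the half-life of the corresponding treatment" before ECD, up to the end of the prior week. Section 7.3.6.5 requires the Unexposed Cohort to have no study biologic "from 5 times the half-life of each medication prior to ECD through the end of pregnancy". Section 7.3.3.1 anchors the oral JAK-inhibitor exclusion on ECD as well.

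Section 7.3.6.2 runs the weekly cohorts from Week 2 to Week 40. Section 7.7.4 treats the absence of a claim as the absence of use.

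Linked claims-EHR sources are handled differently. There 7.3.2 requires pharmacy coverage for the whole pregnancy period, which Table 1 starts at ECD minus 5 half-lives, and gives capture of the cohort-defining drugs as the reason.

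**The concern.** ECD does not move, but cohort entry does. As the entry week rises, the 183 required days slide forward and eventually leave part of the drug-free window outside required enrolment. Because no claim counts as no use, unenrolled time passes as drug-free.

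Two errors become possible in claims-only sources:

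- A woman who used a study biologic around conception under a previous insurer, and has no dispensing in the new plan, can be classed as Unexposed.
- A woman continuing treatment can have her first dispensing in the new plan taken as her first dose. This gives her too late an entry week and undoes the gestational-week alignment on which the sequential design rests.

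The concurrent-exposure exclusion (7.3.3.2) can be missed in the same way. Table 2 shows which outcomes use the later cohorts: live birth, stillbirth and SGA birth to Week 40, preterm birth to Week 36, and, to a lesser degree, spontaneous abortion and elective termination to Week 19.

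**Working it through.** **The plan's own windows.** Appendix D, rounded up to whole days: nemolizumab 5 × 18.9 = 94.5, giving 95; lebrikizumab 5 × 24.5 = 122.5, giving 123; tralokinumab 5 × 21 = 105 (15 weeks); dupilumab 5 × 14 = 70 (10 weeks). All four agree with the protocol.

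**Time scale.** Let LMP be day 0. Table 1 gives ECD as "Estimated as LMP + 14 days", so day 14. For the entry day, 7.3.6.1 gives the pattern: "Cohort entry among the Week 8 nemolizumab and comparator cohorts will be set to 8 weeks' + 0 days". Week w therefore enters on day 7w.

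**Condition for full coverage.** Required enrolment starts on day 7w − 183. The drug-free window starts on day 14 − H, where H is 5 half-lives. The window is fully covered only if 7w − 183 ≤ 14 − H, that is, w ≤ (197 − H)/7.

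| Drug | H (days) | (197 − H)/7 | Last week fully covered | First week with a gap | Weekly cohorts with a gap (of 39) |
|---|---|---|---|---|---|
| Lebrikizumab | 123 | 10.6 | 10 | 11 | 30 |
| Tralokinumab | 105 | 13.1 | 13 | 14 | 27 |
| Nemolizumab | 95 | 14.6 | 14 | 15 | 26 |
| Dupilumab | 70 | 18.1 | 18 | 19 | 22 |

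Counting the entry day inside the 183 (a look-back of 182 days) leaves these weeks unchanged.

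**Size of the gap.** Days not covered = 7w − 197 + H.

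- Nemolizumab: Week 15, 3 of the 95 pre-ECD days; Week 20, 38 (40%); Week 24, 66 (69%); Week 28, 94 (99%).
- Week 29: enrolment starts on day 203 − 183 = 20, which is ECD + 6. From here conception itself may be unobserved.
- Week 40: enrolment starts on day 280 − 183 = 97, the last day of the first trimester in Table 1.
- Malformation cohorts (Weeks 2–13): only lebrikizumab is short, by 3 days at Week 11, 10 at Week 12 and 17 at Week 13, out of 123.

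**Do the planned sensitivity analyses close it?** Section 7.7.3.5.4 shortens the pre-ECD window. For nemolizumab the same formula gives full coverage through Week 20 at 3 half-lives ((197 − 57)/7 = 20), Week 24 at 1.5 half-lives ((197 − 29)/7 = 24) and Week 28 for post-ECD dispensings only (197/7 = 28.1). None covers Weeks 29–40. Requiring two or more dispensings does not reveal earlier ones that were never seen.

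**The case against.** The strongest reply is about scale, and much of it stands.

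This is a minimum-eligibility rule. A reader might infer that periconceptional exposure is unobservable for everyone in the later cohorts. The documents do not support that: women enrolled for longer are fully observed, the nemolizumab gap is nil through Week 14 and partial in Weeks 15–28, and linked claims-EHR sources already have an ECD-anchored pharmacy rule. The count of 30 of 39 weekly cohorts with a gap for at least one drug is a count of cohorts. It says nothing about the share of pregnancies, and the protocol gives no distribution of entry weeks. The first window also collects every dispensing from 5 half-lives before ECD.

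Several events must coincide for a woman to be wrongly Unexposed: a change of insurer, prior use of a study biologic, no dispensing seen in the new plan, and enough visible claims to meet the disease algorithm. Table 4 shows a dupilumab dispensing in 209 of 7,264 AD-coded pregnancies (2.9%), though use among moderate to severe patients would be higher. As an illustration, assume that a share c of the Unexposed group carries the full effect of a true RR of 2.5. The observed ratio is 2.5/(1 + 1.5c): 2.39 at c = 3% and 2.17 at c = 10%. These shares are assumptions.

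It can also be said that enrolment duration is a listed covariate (7.4.3.2) considered for the propensity score (7.7.3.1). That part does not stand, because adjusting for enrolment duration cannot correct a misclassified exposure. Section 7.10 mentions plan changes only as limiting follow-up.

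**Conclusion.** The mismatch is real and confined to claims-only sources: the ORD and any claims-only partner. There the required enrolment does not guarantee observation of the drug-free window from the weeks tabulated above, and from Week 29 it does not guarantee observation of conception. The primary malformation analysis is nearly untouched.

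Three stronger inferences should be resisted.

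- **Direction of bias.** It is not uniformly toward no effect. Contamination of the Unexposed group would usually pull that way, but misdated entry can occur in both the nemolizumab and the active-comparator arm, and its direction is undetermined.
- **JAK-inhibitor exclusion.** It cannot be fully checked from Week 29, whatever the half-life. The protocol does not give those half-lives, so nothing can be said about earlier weeks.
- **Number misclassified.** It cannot be computed, because the protocol has no data on when women join the plan.

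The result assumes that entry falls on day 7w and that no enrolment rule beyond 7.3.2 applies to claims sources; none appears in the protocol. It should be corrected before the final extraction, which Section 4 dates from December 2032. The protocol already accepts the principle for linked sources. It calls that linked requirement the shorter one, yet for nemolizumab it starts earlier than the claims rule from Week 15 on, so the two need reconciling.

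**What to change.** In 7.3.2, for claims sources, require continuous medical and pharmacy enrolment from the earlier of (a) 183 days before cohort entry and (b) 123 days before ECD, through cohort entry. The 123 days are the longest 5-half-life window in Appendix D. This leaves no uncovered day for any of the four biologics in any weekly cohort.

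A single rule of 183 days before ECD is simpler but not safe. The first exposure window opens before ECD, and if entry is dated at a dispensing 95 days before ECD, only 183 − 95 = 88 days of baseline would be guaranteed.

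The cost is some women who joined the plan during or shortly before pregnancy. Nothing changes through Week 10. The look-back grows by 3, 10 and 17 days in Weeks 11–13 and reaches 280 − (14 − 123) = 389 days at Week 40, against 183 now. The losses therefore fall almost entirely in later cohorts. No sample-size figure changes by formula, and the number of pregnancies lost cannot be computed from the protocol.

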7.3.6.7 Follow-up

For each weekly cohort, pregnancies will be followed from the date after cohort entry until the earliest of the end of pregnancy, disenrollment from the health plan (for claims databases), 8 weeks with no clinical activity recorded (for the linked claims-EHR database or EHR-only databases) or the end of the study period (31 March 2032 or latest data available). Each linked infant will be followed from delivery until the earliest of end of first year of life, disenrollment from the health plan (for claims databases), 8 weeks with no clinical activity recorded (for the linked claims-EHR database or EHR-only databases) or the end of the study period. Follow-up for spontaneous abortion and elective termination will be censored at 20 weeks' gestation, and follow-up for preterm birth will be censored at 37 weeks' gestation. The censoring events for each outcome are summarized in [Table 2](#).

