7.5 Study Size

Table 3 presents the minimum number of nemolizumab exposed pregnancies required to detect relative risks equal to or greater than 2.0, 2.5, or 3.0 for a comparative analysis of each of the study outcomes, assuming a ratio of 1:4 exposed to unexposed, 80% power, a 2-sided alpha of 0.05, and the referenced outcome prevalences. For infant outcomes, the minimum number of nemolizumab-exposed livebirths was calculated, and the number of nemolizumab-exposed pregnancies was derived from these counts based on the prevalence of live birth. For the primary outcome MCM, a study size of 214 live births with linked infants exposed to nemolizumab in the first trimester exposure window would provide an 80% power to detect a RR of 2.5, and 133 live births with linked infants exposed to nemolizumab in the first trimester exposure window would provide 80% power to detect a RR of 3. Assuming 80% of pregnancies have an observed outcome and 76% of observed outcomes are live births, an estimated 352 pregnancies exposed to nemolizumab during the first trimester would need to be accrued to detect a RR of 2.5 and 219 exposed pregnancies to detect a RR of 3. With a 1:4 ratio of exposed to unexposed, this corresponds to 1,408 pregnancies (for 2.5) or 876 (for 3) in each comparator group.

Table 3 Sample size required for 80% power to detect effect estimates for pregnancy and infant outcomes, with 1:4 matching¹

Outcome	Prevalence of Outcome	Relative Risk	Nemolizumab Exposed Pregnancies Needed	Nemolizumab Exposed Live Births Needed
MCM	3% ²	2	709	431
		2.5	352	214
		3	219	133
Ectopic pregnancy	1-2%	2	877	N/A
		2.5	438	
		3	275	
Elective termination	21%	2	45	N/A
		2.5	21	
		3	12	
Preterm birth, SGA birth	10% ^{3,4}	2	190	115
		2.5	94	57
		3	56	34
Spontaneous abortion	14% ⁵	2	77	N/A
		2.5	37	
		3	22	
Stillbirth	1% ⁶	2	1,324	N/A
		2.5	662	
		3	415	

Abbreviations: N/A, not applicable; SGA, small for gestational age

¹ Calculations were performed via www.OpenEpi.com using the Fleiss method, as described in Fleiss JL. Statistical Methods for Rates and Proportions. John Wiley & Sons, 1981.

² March of Dimes. Perinatal Data Snapshot: United States Birth Defects. 2015; http://www.marchofdimes.org/peristats/pdflib/999/pds_99_4.pdf.

³ Centers for Disease Control and Prevention. Quick Stats: Percentage of Small for gestational-Age Births, by Race and Hispanic Ethnicity—United States, 2005. MMWR. 2008;57(50):1359. <https://www.cdc.gov/mmwr/preview/mmwrhtml/mm5750a5.htm>.

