MCMs will be identified in live born infants, and study drug exposure will be assessed in the first trimester. However, the exact timing of the development of malformations is typically unknown. Additionally, while the use of ICD-10-CM Z3A codes to estimate LMP has been shown to be accurate ([Chomistek et al., 2023b](#)), not all pregnancies have Z3A codes, and some degree of measurement error is expected in estimating the beginning of pregnancy. The resulting exposure misclassification due to estimated LMP is not expected to be differential with respect to exposure. A sensitivity analysis will explore alternative exposure windows that are more conservative.

It is possible that selection bias may arise due to differential loss to follow-up (i.e., if pregnant women who receive nemolizumab are more or less likely to be lost to follow-up than those who are exposed to other AD/PN treatments or who are unexposed), though we expect censoring to be non-differential with respect to exposure and outcome status. To check this assumption, we will compare the baseline characteristics of pregnancies with an observed outcome versus those who were censored before the end of pregnancy. We will also describe the frequency of censoring events according to nemolizumab exposure status.

Residual confounding is always a concern in observational studies. While propensity score models can account for a large number of measured pre-specified and empirically derived variables, some variables may have a greater degree of misclassification, and some confounders may not be measured. For example, due to ICD-10 coding limitations, claims data tend to have incomplete capture of smoking status. However, the degree of residual confounding due to unmeasured factors may be reduced if proxies of unmeasured factors are included in the models ([Guertin et al., 2016](#)). A quantitative bias analysis will assess the impact of residual confounding on the observed results.

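### In linked claims-EHR sources, eligibility requires pharmacy coverage up to the pregnancy outcome, which over-selects early-ending pregnancies and biases early-loss frequencies upward

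*Protocol*

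**What the plan says.** Protocol 7.3.2 sets different coverage rules for the two kinds of source.

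- **Claims sources:** "complete medical and pharmacy benefit coverage from 6 months before and including cohort entry". Nothing is required after entry. Under 7.3.6.7 follow-up then ends at "disenrollment from the health plan (for claims databases"), among other events.
- **Linked claims-EHR sources (Market Clarity):** "Pharmacy (but not medical) coverage during the full pregnancy period", with a pointer to Table 1, where the pregnancy period "Begins at ECD minus 5 times the half-life of the treatment Ends at pregnancy outcome". The stated purpose is that this "will be required to ensure dispensings of cohort defining drugs are captured". In 7.3.6.7 and Table 2 the loss-to-follow-up rule for these sources is "8 weeks with no clinical activity recorded (for the linked claims-EHR database or EHR-only databases"). Loss of pharmacy coverage is not a censoring event.

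7.3.2 explains the linked rule by saying that it asks for less continuous enrolment than the claims rule. For selection through loss to follow-up, 7.10 offers one check on who is lost: "we will compare the baseline characteristics of pregnancies with an observed outcome versus those who were censored before the end of pregnancy". It also promises to describe the frequency of censoring by exposure status.

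**The concern.** An inclusion criterion should be decidable at cohort entry. This one is decided at the end of pregnancy, and it is easier to meet the sooner the pregnancy ends. A woman who loses pharmacy coverage before her outcome is removed from the study. In a claims source the same woman would contribute time up to disenrolment and then be censored.

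Three things follow. The frequency of each pregnancy outcome is part of the first objective, and in linked sources the frequencies of early endings would be too high. The comparison in 7.10 cannot reveal this, because the women concerned are excluded before anyone is counted as observed or censored. And frequencies from linked sources would not be comparable with those from the Optum Research Database, where the rule does not apply. The rule also sits badly with the design in 7.1, which aligns entry by gestational week to emulate a target trial.

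**Working it through.** **Figures the protocol gives.** It gives no coverage-loss rate. The nearest figure is in 7.5: "Assuming 80% of pregnancies have an observed outcome and 76% of observed outcomes are live births". This reproduces the study size: 214 / (0.80 × 0.76) = 351.97, stated as 352; and 133 / 0.608 = 218.75, stated as 219. The 80% is a general assumption about observed outcomes, not a rate of pharmacy-coverage loss, so the loss rate is varied below as an assumption.

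**Length of coverage required** (Table 1; 95 days for nemolizumab from Appendix D; ECD at 2 weeks' gestation):

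- Ending at 9 weeks: 95 + (63 − 14) = 144 days.
- Ending at 39 weeks: 95 + (273 − 14) = 354 days.
- Claims sources (7.3.6.6): 183 days.

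The linked rule exceeds 183 days once a nemolizumab pregnancy passes 183 − 95 = 88 days after ECD, which is about 12.6 + 2 = 14.6 weeks' gestation. The claim that it is the shorter requirement is untrue for most pregnancies.

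**Effect on a frequency.** Inputs: spontaneous abortion 14% (Table 3). Assumed: losses at 10 weeks, all other pregnancies to 39 weeks, and a constant rate of coverage loss from ECD, unrelated to outcome, with a fraction L lost by 39 weeks. The probability of qualifying is 1 − L for the 37-week span and q = (1 − L)^(8/37) for the 8-week span. The frequency among qualifiers is

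0.14q / [0.14q + 0.86(1 − L)].

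| L (assumed) | q, loss at 10 wk | 39 wk | 14% reads |
|---|---|---|---|
| 5% | 0.989 | 0.95 | 14.5% |
| 10% | 0.977 | 0.90 | 15.0% |
| 20% | 0.953 | 0.80 | 16.2% |
| 30% | 0.926 | 0.70 | 17.7% |

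For L = 20%: 0.14 × 0.953 = 0.1334; 0.86 × 0.80 = 0.688; 0.1334 / 0.8214 = 0.162. The share reaching 39 weeks falls correspondingly, from 86% to 83.8%. With losses at 8 weeks and L = 30%, q = 0.944 and the frequency reads 18.0%.

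Expressing incidence per person-time does not remove the effect. In a simulation of the same rule, the rate among qualifiers was about 8%, 17% and 28% too high at 10%, 20% and 30% loss, relative to censoring at coverage loss.

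**Effect on ratios.** With equal loss in both cohorts, a true ratio of 1 stays 1. A true ratio of 2 at L = 20% reads [0.28 × 0.953 / (0.28 × 0.953 + 0.72 × 0.80)] / 0.162 = 0.317 / 0.162 = 1.95. With unequal loss, a true ratio of 1 shifts: 20% in the exposed against 10% in the comparator gives 0.162 / 0.150 = 1.08. With 10% against 30% it gives 0.150 / 0.177 = 0.85, or 0.87 by simulation.

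**Effect on the primary outcome.** Major congenital malformations (MCMs) are assessed in live births, which have similar gestations. At L = 20% the weekly rate is −ln(0.80)/37 = 0.0060. Even if every affected infant were born 3 weeks earlier than the others, retention would differ by exp(3 × 0.0060) − 1, about 2%.

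**Denominator.** Suppose the same women are kept and censored instead, with L = 20%. Losses divided by observed outcomes are again 0.1334 / 0.8214 = 16.2%, and losses divided by all entrants are 13.3%. Only an estimate that accounts for censoring returns 14%.

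**The case against.** The strongest defence is that the rule has a purpose. Unexposed status (7.3.6.5), the JAK-inhibitor exclusion (7.3.3.1) and the teratogen exclusion (7.3.3.3) all run to the end of pregnancy, and dispensings cannot be seen after coverage stops. This stands as a real cost of changing the rule. It does not justify the rule as written, because the claims sources apply the same definitions without it and the weekly design classifies exposure at each entry week.

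It is also fair that the flow chart in 7.7.3.2 can show how many pregnancies drop out at the coverage step. A count of that kind does not correct the frequencies.

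Three stronger readings are tempting, and the protocol does not support them.

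- A reader might take the 80% and 76% in 7.5 as the protocol's own coverage-loss inputs and derive a single figure for the bias. The 80% covers every reason an outcome goes unobserved and is not specific to linked sources. The 76% is a share of observed outcomes, so it already applies after loss and cannot serve as the share before loss.
- A reader might infer that the nemolizumab comparisons, including the primary one, are compromised. Estimates are made within each source before meta-analysis, ratios hardly move under equal loss, and nothing in the protocol suggests that loss differs by cohort.
- A reader might say that the start of the window is undefined for the Unexposed Cohort, because Table 1 refers to a single treatment. Section 7.3.6.5 applies five half-lives of each medication, which with Appendix D implies 123 days. Table 1 is loosely worded, and the other sections largely settle it.

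**Conclusion.** The point holds for descriptive frequencies in linked claims-EHR sources. 7.3.2 read with Table 1 makes eligibility depend on coverage up to the outcome, no other section repairs this, and the limitations in 7.10 do not mention it. The direction is upward for spontaneous abortion, elective termination and ectopic pregnancy, and downward for live birth. It holds unless coverage loss is concentrated in pregnancies that end early.

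The size is an assumption range: about 14.5% to 18% for a true 14%, if 5% to 30% lose pharmacy coverage by term at a constant rate. With less loss it approaches zero. Ratios are materially affected only if coverage loss differs between cohorts, and the MCM comparison is little affected. Optum Research Database results are untouched. Separately, the stated rationale that linked sources need less continuous enrolment is wrong for most pregnancies (354 days against 183 for a nemolizumab pregnancy ending at 39 weeks).

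**What to change.** Make three changes for linked claims-EHR sources.

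1. In 7.3.2, require pharmacy coverage from one pre-ECD start, the same for all three cohorts, through cohort entry. The start should cover the longest five-half-life window in Appendix D, 123 days, in line with 7.3.6.5. A start tied to the index drug alone (95 days for nemolizumab, 70 for dupilumab) would not span the windows for lebrikizumab (123) and tralokinumab (105), which 7.3.6.1 also requires to be clear. Delete or correct the remark about shorter enrolment.
2. In Table 2 and 7.3.6.7, add loss of pharmacy coverage as a censoring event for these sources. The 7.10 check will then see these women.
3. In 7.7.3.2, state that the incidence of pregnancy outcomes is estimated by person-time or survival-type methods that account for censoring, not as a share of observed outcomes. Without this the second change would leave the same inflation.

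The cost is wording only, and Market Clarity counts do not begin until the 2029 PSUR. More pregnancies enter with partial follow-up, and a few with short pre-ECD coverage are lost. Exposure to JAK inhibitors, teratogens or comparator drugs after coverage ends cannot be verified. The claims sources already carry that limitation, and 7.10 should state it.
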